5.5 Removal of Subjects from Study Treatment or Study

Subjects can be taken off the study treatment and/or study at any time at their own request, or they may be withdrawn at the discretion of the investigator for safety, behavioral or administrative reasons. The reason(s) for discontinuation will be documented and may include:

- 5.5.1 Subject voluntarily withdraws from treatment (follow-up permitted);
- 5.5.2 Subject withdraws consent (termination of treatment and follow-up);
- 5.5.3 Subject is unable to comply with protocol requirements; patients must be withdrawn from the trial and replaced if they failed to receive the SABR treatment. Any patient with at least one cycle of Nivolumab and SABR will be included in the analysis.
- 5.5.4 Subject demonstrates disease progression (unless continued treatment with Nivolumab is deemed appropriate at the discretion of the medical oncologist);
- 5.5.5 Subject experiences toxicity that makes continuation in the protocol unsafe;

- 5.5.6 Treating physician judges' continuation on the study would not be in the subject's best interest;
- 5.5.7 Subject becomes pregnant (pregnancy to be reported along same timelines as a serious adverse event);
- 5.5.8 Development of second malignancy (except for basal cell carcinoma or squamous cell carcinoma of the skin) that requires treatment, which would interfere with this study;
- 5.5.9 Lost to follow-up. If a research subject cannot be located to document survival after a period of 2 years, the subject may be considered "lost to follow-up." All attempts to contact the subject during the two years must be documented .

5.6. Subject Replacement: Subject replacements are allowed in the following situations:

- 5.6.1 If the subjects decide to withdraw from the study without finishing the course of SAbR
- 5.6.2 If the subjects decide to withdraw from the study or lost to follow up (for reasons of death from other causes, moving to other state etc.) or refuse follow up scans leading to <2 follow-up scans (making it impossible to assess the primary endpoint of the trial)

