2.2 Secondary Objectives

- 2.2.1 RR based on ir-RECIST
- 2.2.2 To evaluate overall survival (OS), which is defined as the time between date of registration and the date of death due to any cause. In analyzing OS, we will take into account the MSKCC prognostic criteria for mRCC and compare our data to historical controls in the appropriate risk category
- 2.2.3 To evaluate progression free survival (PFS), which is defined as the time between date of registration and the first date of documented disease progression or date of death due to any cause
- 2.2.4 To evaluate complete response rate, which is defined as the percentage of patients who show complete response as per ir-RECIST criteria
- 2.2.5 To evaluate time to progression (TTP), which is defined as time between date of registration and date of documented progression.
- 2.2.6 To evaluate median response duration, which is defined as the time between the date a response (CR or PR) was first seen until date of progression
- 2.2.7 To evaluate the tolerability and toxicity as measured according to CTCAE v4.0.
- 2.2.8 To measure the improvement in health-related quality of life (HR-QoL)

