6.1.7 Progression-Free Survival

Progression-free survival (PFS) is defined as the duration of time from the date of registration to time of progression or date of death due to any cause.

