11.2 Sample Size and Accrual

The first six patients assigned will be assessed for feasibility, safety, and toxicity for interim safety of the trial 8 weeks post-registration. If more than 3 patients experience \geq Grade 3 SAE attributed to the SAbR+Nivolumab out of 6 patients, the study will be held until approval from DSMC.

The previous studies show that the maximum RR for mRCC patients treated with Nivolumab is 25%. We expect that the addition of SAbR to Nivolumab will increase the RR to 50% i.e. a 100% increase compared to the historical RR to Nivolumab alone. In our current ongoing phase II clinical trial (STU 012013-041) with similar patient population and treatment strategy of SABR + immunotherapy using IL-2, we are noticing a 53% RR with the combination whereas the historically reported response rate of IL-2 alone treatment is 20% (1). Therefore, we have increased the RR by $>150\%$. Therefore, in oncology clinical trials, it is not uncommon to see such increases since the baseline RR is often low.

The calculation of the sample size is based on the RR. In this phase II trial, we will recruit a total of 19 patients including the 6 patients that will be used for interim safety analysis. A total sample size of 19 achieves 80% power to detect 25% absolute difference in RR (25% vs. 50%) using an exact binomial test at a 0.2 two-sided significance level. To allow for potential subject dropouts, the accrual goal will be increased by an additional 2 patients for a total of 21 patients. The sample size was estimated using a sample size software PASS 14 ("Hintze, J. (2015). PASS 14. NCSS, LLC. Kaysville, Utah, USA. www.ncss.com.")

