11.3 Data Analyses Plans

Exact binomial method will be used to calculate the response rate, toxicity rate, CR rate, and the corresponding 95% confidence interval. [Exact binomial test will be used to investigate if the response rate of the treatment arm is significantly different from that of historical control.](#) PFS and OS will be estimated using the Kaplan-Meier approach along with the 95% confidence interval using Greenwood's formula. One sample log-rank tests will be conducted to investigate if OS or PFS in the treatment arm is significantly different from that of historical control.

Generalized estimating equation (GEE) analysis will be conducted to investigate if there are significant changes in surrogate makers such as CD25, CD71, CD45RO, CD107a, CD54, CD69, Ki67, ICOS/CD278 and PBMC over time. HRQoL, CEA and quality adjusted survival time analysis is described in Section 10.

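### OS and PFS are timed from registration, but patients who never reach SABR are withdrawn and replaced, which tilts both historical comparisons toward benefit: slightly for OS, by an uncertain amount for PFS

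*Combined protocol and SAP*

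**What the plan says.** - **Clock.** Section 2.2 defines OS as "the time between date of registration and the date of death due to any cause". Section 6.1.7 defines PFS as "the duration of time from the date of registration to time of progression or date of death due to any cause".
- **Who is analysed.** Section 5.5.3 states that "patients must be withdrawn from the trial and replaced if they failed to receive the SABR treatment". Its next sentence includes in the analysis any patient with one or more nivolumab cycles and SABR, without limiting this to response.
- **Test.** Section 11.3: "One sample log-rank tests will be conducted to investigate if OS or PFS in the treatment arm" differs from the historical control. It names no OS or PFS population, significance level, landmark or delayed entry. The Study Summary gives the comparator as nivolumab alone from a published phase III study.
- **When SABR happens.** Section 2.0 puts it one week after the first dose. Section 4.1 puts it two weeks after the second dose, Section 4.3 between the second and fourth doses, and Section 5.2 after the first cycle. These statements must be reconciled.

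**The concern.** A patient who dies before SABR, or whose progression stops SABR from being given, leaves the trial and is replaced by someone who did reach SABR. The replacement's time from registration to SABR is nevertheless counted as time at risk. In a one-sample log-rank test the expected events are the historical cumulative hazard summed over each patient's time at risk. Expected events therefore include weeks from which some or all of the events have been removed by selection. Observed falls below expected even if SABR adds nothing.

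The error has one direction. In a single-arm trial the historical comparison is the only inference available on OS and PFS. If withdrawal from the trial is applied literally, later outcomes of the replaced patients may not be collected, and the bias could not then be corrected afterwards.

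**Working it through.** **The plan's own figure.** Section 11.2 sizes the trial on response, 25% versus 50%, "using an exact binomial test at a 0.2 two-sided significance level". With an upper tail of 0.10, the smallest n with at least 80% power is 19: reject at 8 or more responses, upper-tail alpha 0.0775, power 0.820 (n = 18 gives 0.760). The stated 19 reproduces. No power or alpha is stated for OS or PFS.

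**Inputs**
- Historical medians (Section 1.4.2): OS 25 months; PFS 4 to 4.6 months, with 4.3 used as the midpoint.
- n = 19; accrual uniform over 60 months plus 36 months of follow-up (Study Summary).
- Assumed: exponential times; dosing every 3 weeks, as Section 1.4.2 cites for the historical data; registration and first dose on the same day. SABR then falls at about week 1 (Section 2.0), week 5 (Section 4.1) or up to week 9 (Section 4.3), that is g = 0.23, 1.15 or 2.07 months.
- Assumed: one-sided Z < -1.96, since no alpha is given.

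**Formulas.** λ = ln 2 / median. E = λ × total time at risk, and Z = (O − E)/√E. The chance of an event before SABR is p = 1 − exp(−λg). Let f be the share of pre-SABR events that prevent SABR. Ignoring censoring, expected events per analysed patient are (1 − f·c)/(1 − f·p), where c = 1 − (1 − p)(1 + λg), and O/E is the reciprocal. At f = 1 this is 1/(1 + λg).

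**OS, f = 1** (a death before SABR always prevents it). p = 0.006, 0.031 and 0.056 at weeks 1, 5 and 9, so about 0.1, 0.7 and 1.2 of 21 registered patients would die before SABR. The built-in gain in the median equals g.

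| SABR at | O/E | Tail Z < -1.96 |
|---|---|---|
| No restriction | 1.00 | 1.5% |
| Week 1 | 0.99 | 1.7% |
| Week 5 | 0.96 | 2.1% |
| Week 9 | 0.93 | 2.6% |

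At a nominal 10% tail, matching the response test, the figures are 8.2% without the restriction and 8.8%, 10.6% and 12.8% with it.

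**PFS, median 4.3 months.** λ = 0.6931/4.3 = 0.161. At week 5, λg = 0.185 and p = 0.169; at week 9, λg = 0.334 and p = 0.284. For example, at week 5 with f = 0.5: c = 1 − 0.831 × 1.185 = 0.015, expected events = (1 − 0.008)/(1 − 0.085) = 1.084, and O/E = 0.92.

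| Share f preventing SABR | Week 5: O/E, tail | Week 9: O/E, tail |
|---|---|---|
| 25% | 0.96, 2.2% | 0.94, 2.5% |
| 50% | 0.92, 2.9% | 0.88, 4.4% |
| 100% (upper bound) | 0.84, 6% | 0.75, 16% |

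The unrestricted tail is again about 1.5%. At week 1, even f = 100% gives O/E 0.96 and a tail of 2.0%.

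**A guide to f.** On the protocol's medians, deaths make up about 0.031/0.169 = 19% of pre-SABR PFS events at week 5 and 0.056/0.284 = 20% at week 9. A 25% share is therefore deaths plus a few progressions that stop SABR.

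**Check of the mechanism.** Counting time at risk only from SABR in the f = 1 model returns O/E to 1.00 and the tail to about 1.5%. Tails are simulated, so the last digit moves by about 0.1 to 0.2 percentage points between runs.

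**The case against.** **Progression rarely prevents SABR.** Imaging is every 8 to 12 weeks from registration (Sections 4.4, 5.3), so with SABR at week 1 or 5 no scheduled scan comes first. Progression needs a second scan more than 6 weeks later (Section 6.1) before the decision to stop treatment (Section 4.2.1.1), and treatment beyond progression is allowed (Sections 2.1, 5.5.4). A patient who progresses early and still receives SABR stays in the analysis with the event counted. This stands. A reader might infer that no PFS event can be observed before SABR, and so take 6% or 16% as the false-positive rate. The documents support those figures only as an upper bound. Some progressions could still prevent SABR: confirmed cord compression, or fracture away from a treated site, counts as progression without waiting for a scheduled scan (Sections 6.1.4.5, 6.1.4.6).

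**OS is barely affected.** Largely true. Patients with life expectancy under 6 months are excluded (Section 3.2.9), so early deaths may be fewer than an exponential curve implies.

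**The plan does not expressly exclude these patients from OS and PFS.** Correct: the exclusion follows from reading the withdrawal, replacement and inclusion statements together. Section 4.5 keeps patients removed from therapy in follow-up. It does not, however, return patients withdrawn from the trial to the analysis. Response and safety each have a stated set (Sections 6.1.1, 6.2); OS and PFS have none.

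**Conclusion.** Followed as written, the plan biases both historical comparisons toward benefit. For OS the effect is small: O/E 0.93 to 0.99, and a tail that rises from about 1.5% to at most 2.6%. For PFS it ranges from negligible, with SABR at week 1 or a low share of SABR-preventing events, to a doubling or tripling of the tail at a 50% share with SABR at week 5 or 9. The share is unknown, and the protocol's scan and confirmation rules make a partial share likelier than 100%.

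The sizes rest on exponential times, 3-weekly dosing (study dosing follows institutional guidelines), a threshold chosen here, and a historical curve that runs from its own study entry without a landmark. Any gap between registration and first dose would lengthen the protected time. These are secondary endpoints. A reader might infer that the sample size is undermined; it is not, since 19 rests on the response rate alone.

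**What to change.** In Sections 5.5.3 and 11.3, state that:
- OS and PFS are analysed in all registered patients from registration, or in all who start nivolumab with the clock starting at the first dose;
- replacement, including under Section 5.6, applies only to the response-evaluable set;
- patients who do not receive SABR stay in survival and progression follow-up.

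If a SABR-treated set is also shown, label it supportive. For OS, enter patients at risk at the SABR date. For PFS, either apply a landmark at SABR to patients then progression-free, or state that the estimate is conditional on reaching SABR. Plain delayed entry for PFS would drop irradiated patients who had already progressed, and so discard real events.

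Reconcile the SABR timing statements in Sections 2.0, 4.1, 4.3 and 5.2, because they determine the length of the protected period.

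The cost is plan wording, follow-up of a few replaced patients, and slightly less favourable OS and PFS estimates. The response-rate sample size does not change.

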2.4 Endpoints

- 2.4.1 **Response:** Treatment response will be measured using both the RECIST and immune related RECIST criteria (ir-RECIST), a minor modification of RECIST 1.1 for immunotherapy [89]. Radiated lesions will be excluded from target lesions.
- 2.4.2 **Death:** Death due to any cause, although in mRCC patient population, the overwhelming majority is expected to be secondary to disease progression.
- 2.4.3 **Progression:** Progression will be defined according to the ir-RECIST criteria and verified by a second set of imaging at least 6 weeks apart.
- 2.4.4 **Immune Response:** Immune response will be measured using ELISpot assay, T-cell proliferation assay and ELISA.
- 2.4.5 **Toxicity:** Toxicity will be measured using CTAE v4.0

- 2.4.6 HR-QoL:** HR-QoL will be measured using FACT-G, EQ-5D and FKSI questionnaires at baseline, and at different time-points during treatment and follow up
- 2.4.7 Cost-effectiveness analysis:** Health care utilization data needed to assess costs will be obtained from patients' insurance claims during and after treatment. Markov modeling with probabilistic sensitivity analysis will be used to correlate quality-adjusted survival and cost.

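### Section 5.6.2 treats an early death from other causes as loss to follow-up and lets the patient be replaced, in conflict with the any-cause death definitions of OS and PFS and with 5.5.3 and 5.5.9

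*Combined protocol and SAP*

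**What the plan says.** Section 5.6 opens with "Subject replacements are allowed in the following situations". Item 5.6.2 covers patients who withdraw, patients who are "lost to follow up (for reasons of death from other causes, moving to other state etc".), and patients who "refuse follow up scans leading to <2 follow-up scans (making it impossible to assess the primary endpoint of the trial").

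Four other parts of the protocol bear on the same patient:

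- **Death as an endpoint.** Section 2.2.2 defines OS as "the time between date of registration and the date of death due to any cause". Sections 2.2.3 and 6.1.7 count any-cause death as a PFS event. Section 2.4.2 reads "Death due to any cause, although in mRCC patient population, the overwhelming majority is expected to be secondary to disease progression".
- **Loss to follow-up.** Section 5.5.9 applies the term "If a research subject cannot be located to document survival after a period of 2 years".
- **Who is analysed.** Section 5.5.3 states "Any patient with at least one cycle of Nivolumab and SABR will be included in the analysis". Section 6.1.1 limits the response-evaluable set to patients with SABR, one nivolumab cycle and at least two disease re-evaluations.
- **Analysis.** Section 11.3 specifies Kaplan-Meier estimates and one-sample log-rank tests against the historical control for OS and PFS. It gives no analysis set for them and no censoring rule, and it does not say whether replaced patients stay in.

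**The concern.** A known death is an observed outcome. Section 5.6.2 puts it in the same class as moving to another state, where the outcome is unknown. The same patient can then be an OS and PFS event under one section and a replaced, lost patient under another. Because replacement is optional and the cause of death is judged after the event, the choice is made once the outcome is known, in a single-arm trial compared with a historical rate.

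If early deaths are dropped or censored, OS and PFS look better than they are. If the patient is replaced for response, a certain non-responder gives way to someone who may respond. Both effects run in favour of the combination. The term for other causes is not defined either, so nothing clearly keeps a treatment-related death out of the replacement rule.

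**Working it through.** **1. The sections side by side.** Take a patient who receives SABR and one nivolumab cycle and dies of a non-cancer cause before the second follow-up scan.

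| Section | Status of this patient |
|---|---|
| 2.2.2, 2.4.2 | OS event on the date of death |
| 2.2.3, 6.1.7 | PFS event on the date of death, if no earlier progression |
| 5.5.3 | Included in the analysis |
| 5.5.9 | Not lost to follow-up: survival status is known |
| 5.6.2 | Lost to follow-up; may be replaced |
| 6.1.1 | Not evaluable for response |
| 11.3 | Silent on the OS/PFS set and on censoring |

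I read the condition of fewer than two scans as applying to every limb of 5.6.2. This is the narrower reading; if it applied only to scan refusal, later deaths would be caught as well.

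**2. The plan's sample size.** Inputs from 11.2: 25% against 50%, exact binomial test, two-sided 0.2, 80% power. With 0.10 in the upper tail and n = 19, the test rejects at 8 or more responders. Then P(X ≥ 8 | 0.25) = 0.0775 and P(X ≥ 8 | 0.50) = 0.8204. At n = 18 the power is 0.7597. The figure of 19 reproduces.

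**3. Window for the clause.** Section 5.3 sets follow-up every 8-12 weeks from registration, so two scans take 16-24 weeks, or 3.68-5.52 months. Section 1.4.2 gives a historical median OS of 25 months. I assume exponential survival.

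- P(death by 16 weeks) = 1 − exp(−ln 2 × 3.68/25) = 9.7%
- P(death by 24 weeks) = 1 − exp(−ln 2 × 5.52/25) = 14.2%
- Of 19 patients: 1.8 to 2.7 deaths from any cause

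**4. Share that is not due to cancer.** The documents give no figure. At an assumed 10-30%, the number affected runs from 0.10 × 1.8 = 0.2 to 0.30 × 2.7 = 0.8 patients.

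**5. Effect on OS.** The one-sample log-rank statistic is Z = (O − E)/√E. Expected deaths among 19 patients followed for t months are E = 19 × (1 − 0.5^(t/25)). The times are the 2-4 years of median follow-up at which section 4.4 plans to report.

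| t (months) | E | Shift for one death, 1/√E |
|---|---|---|
| 24 | 9.2 | 0.33 |
| 36 | 12.0 | 0.29 |
| 48 | 14.0 | 0.27 |

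This is the shift when a whole death is censored at its own date. Weighted by the 0.2-0.8 patients expected, it is about 0.05 (0.2 × 0.27) to 0.26 (0.8 × 0.33).

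As a survival proportion at the accrual goal of 21: 12-month OS under the historical curve is 0.5^(12/25) = 71.7%, or 15.06 of 21. Dropping one early death gives 15.06/20 = 75.3%.

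**6. Effect on response.** Suppose the result is just positive, 8/19 (42.1%, upper-tail p = 0.0775), after one such patient was replaced. Keeping that patient as a non-responder gives 8/20 (40.0%, p = 0.1018), which no longer meets the 0.10 upper tail. The example depends on the equal-tail reading in step 2, and it is a borderline case chosen for illustration.

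**The case against.** The best defence is that 5.6 is an accrual rule. Its stated reason is that the primary endpoint, response, cannot be assessed; recruiting a substitute does not delete the first patient's death. The OS and PFS definitions are unambiguous, and 5.5.3 can be read as the answer: the treated patient stays in OS and PFS while a substitute restores the number evaluable for response. This reading is reasonable, and replacement is permitted, not required. But nothing in 11.3 selects it, and the lost-to-follow-up label points the other way.

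Three stronger readings are tempting and are not supported:

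- **That the protocol censors these deaths.** A reader might infer this from the label. No censoring rule is written; the defect is that the handling is left open.
- **That fatal toxicity could disappear from the safety results.** Section 4.2.1.1 makes every treated patient evaluable for toxicity, 6.1.1 does so for all subjects from registration, and 6.2 covers everyone given at least one SABR fraction and one nivolumab cycle. Section 7 classes any death in the monitoring period as a serious adverse event, to be notified to the principal investigator within 24 hours and to the monitoring committee within 5 business days. None of these provisions exempts a replaced patient.
- **That toxic deaths are other-cause deaths as written.** The term is undefined. The contrast with disease progression in 2.4.2 makes that reading possible; the neighbouring example of moving away suggests incidental reasons. The text neither includes nor excludes them.

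It is also fair that few patients are at issue. Section 2.4.2 expects the overwhelming majority of deaths to follow progression, so the upper end of the assumed 10-30% may be too high.

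**Conclusion.** The contradiction is real and no other section resolves it. Section 5.6.2 conflicts with 2.2.2, 2.2.3, 2.4.2, 5.5.3, 5.5.9 and 6.1.7, and with 11.3 silent, two analysts could treat the same early death differently and both claim to follow the protocol. If the death is dropped, censored or replaced, the bias favours the combination.

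The expected size is small: fewer than one patient, given exponential survival at the 25-month median, scans on schedule and the assumed non-cancer share. One whole death moved shifts the OS Z by about 0.3, and can matter for response only near the rejection boundary. The point concerns OS, PFS and the response rate; it does not extend to the safety counts. It should be corrected because the rule permits a choice after the outcome is known and the correction is cheap.

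**What to change.** 1. Delete the reference to death from other causes in 5.6.2, and state that a known death is never loss to follow-up and never a ground for replacing a treated patient.
2. In 11.3, state that all patients given SABR and at least one nivolumab cycle stay in the OS and PFS analyses, with death from any cause as an event on its date.
3. In the same place, state that a patient who dies before two follow-up scans counts as a non-responder for RR, unless a response meeting the protocol criteria was already recorded.
4. Reconcile 5.5.3, 5.5.9, 5.6.2 and 6.1.1 with these statements. Changing 5.6.2 alone is not enough, because the two-re-evaluation requirement in 6.1.1 would still remove the patient from the response set.

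The cost is one phrase deleted and a few sentences added. Treatment, visits and the planned sample size do not change. RR, OS and PFS may come out slightly less favourable.
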